3 PARTICIPANT SELECTION

3.1 Eligibility Criteria

- 3.1.1 Patients with locally unresectable or metastatic well-differentiated neuroendocrine tumor of non-pancreatic (ie, carcinoid) origin
- 3.1.2 Participants must have measurable disease, defined as at least one lesion that can be accurately measured in at least one dimension (longest diameter to be recorded for non-nodal lesions and short axis for nodal lesions) as ≥ 20 mm with conventional techniques or as ≥ 10 mm with spiral CT scan, MRI, or calipers by clinical exam. See Section 11 for the evaluation of measurable disease.
- 3.1.3 Patients must have evidence of radiographic disease progression within the past 12 months.
- 3.1.4 Patients who have received at least one line of therapy, which can include somatostatin analog therapy. Participants should be adequately recovered from acute toxicities of prior treatment.
 - Prior somatostatin analog therapy is allowed. Continuation of somatostatin analog therapy is allowed provided that the dose has been stable for 2 months.
 - Prior chemotherapy: Participants must have been off treatment with cytotoxic chemotherapy for at least 14 days prior to registration.
 - Prior biologic therapy: Patients must have discontinued all biologic therapy at least 28 days prior to registration. Duration may be shortened to 14 days for agents with short half-lives.
 - Prior radiolabeled somatostatin analog therapy: Participants must have completed radiolabeled somatostatin analog therapy at least 6 weeks prior to registration.
 - Prior hepatic artery embolization or ablative therapies is allowed if measurable disease remains outside the treated area or there is documented disease progression in a treated site. Prior liver-directed or ablative treatment must be completed at least 28 days prior to registration.
 - Prior radiation therapy: Radiation therapy must be completed per the following timelines
 - i) Radiotherapy to the thoracic cavity or abdomen within 4 weeks prior to registration.
 - ii) Radiotherapy to bone lesions within 2 weeks prior to registration.
 - iii) Radiotherapy to any other site within 4 weeks prior to registration.
- 3.1.5 Age ≥ 18 years.

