11.1.2 Disease Parameters

Measurable disease. Measurable lesions are defined as those that can be accurately measured in at least one dimension (longest diameter to be recorded) as ≥ 20 mm by chest x-ray or ≥ 10 mm with CT scan, MRI, or calipers by clinical exam. All tumor measurements must be recorded in millimeters (or decimal fractions of centimeters).

Malignant lymph nodes. To be considered pathologically enlarged and measurable, a lymph node must be ≥ 15 mm in short axis when assessed by CT scan (CT scan slice thickness recommended to be no greater than 5 mm). At baseline and in follow-up, only the short axis will be measured and followed.

Non-measurable disease. All other lesions (or sites of disease), including small lesions (longest diameter <10 mm or pathological lymph nodes with ≥ 10 to <15 mm short axis), are considered non-measurable disease. Bone lesions, leptomeningeal disease, ascites, pleural/pericardial effusions, lymphangitis cutis/pulmonitis, inflammatory breast disease, abdominal masses (not followed by CT or MRI), and cystic lesions are all considered non-measurable.

Note: Cystic lesions that meet the criteria for radiographically defined simple cysts should not be considered as malignant lesions (neither measurable nor non-measurable) since they are, by definition, simple cysts.

‘Cystic lesions’ thought to represent cystic metastases can be considered as measurable lesions, if they meet the definition of measurability described above. However, if non-cystic lesions are present in the same participant, these are preferred for selection as target lesions.

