Target lesions. All measurable lesions up to a maximum of 2 lesions per organ and 5 lesions in total, representative of all involved organs, should be identified as **target lesions** and recorded and measured at baseline. Target lesions should be selected on the basis of their size (lesions with the longest diameter), be representative of all involved organs, but in addition should be those that lend themselves to reproducible repeated measurements. It may be the case that, on occasion, the largest lesion does not lend itself to reproducible measurement in which circumstance the next largest lesion which can be measured reproducibly should be selected. A sum of the diameters (longest for non-nodal lesions, short axis for nodal lesions) for all target lesions will be calculated and reported as the baseline sum diameters. If lymph nodes are to be included in the sum, then only the short axis is added into the sum. The baseline sum diameters will be used as reference to further characterize any objective tumor regression in the measurable dimension of the disease.

Non-target lesions. All other lesions (or sites of disease) including any measurable lesions over and above the 5 target lesions should be identified as **non-target lesions** and should also be recorded at baseline. Measurements of these lesions are not required, but the presence, absence, or in rare cases unequivocal progression of each should be noted throughout follow up.

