11.1.4 Response Criteria

11.1.4.1 Evaluation of Target Lesions

Complete Response (CR): Disappearance of all target lesions. Any pathological lymph nodes (whether target or non-target) must have reduction in short axis to <10 mm.

Partial Response (PR): At least a 30% decrease in the sum of the diameters of target lesions, taking as reference the baseline sum diameters.

Progressive Disease (PD): At least a 20% increase in the sum of the diameters of target lesions, taking as reference the smallest sum on study (this includes the baseline sum if that is the smallest on study). In addition to the relative increase of 20%, the sum must also demonstrate an absolute increase of at least 5 mm. (Note: the appearance of one or more new lesions is also considered progressions).

Stable Disease (SD): Neither sufficient shrinkage to qualify for PR nor sufficient increase to qualify for PD, taking as reference the smallest sum diameters while on study.

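### Section 3.1.2 lets a 10 mm lymph node count as measurable for entry, while 11.1.2 requires 15 mm, so a patient with no target lesion and no route to partial response can be enrolled

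*Combined protocol and SAP*

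**What the plan says.** **Entry.** Section 3.1.2 requires at least one accurately measurable lesion and states the dimension to use: "longest diameter to be recorded for non-nodal lesions and short axis for nodal lesions". The size limits follow, 20 mm by conventional techniques "or as ≥ 10 mm with spiral CT scan, MRI, or calipers by clinical exam". Nodes get no limit of their own. The criterion ends with a pointer: "See Section 11 for the evaluation of measurable disease".

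**Response assessment.** Section 11.1.2 sets a different limit for nodes: "a lymph node must be ≥ 15 mm in short axis when assessed by CT scan". Smaller nodes are placed outside measurable disease: "pathological lymph nodes with ≥ 10 to <15 mm short axis), are considered non-measurable disease". Target lesions are drawn from measurable lesions only ("All measurable lesions up to a maximum of 2 lesions per organ and 5 lesions in total"), and partial response under 11.1.4.1 is "At least a 30% decrease in the sum of the diameters of target lesions". In 11.1.4.4 the table for participants with non-measurable disease offers complete response, non-CR/non-PD, not evaluated and progression. It has no partial-response row.

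**Endpoint.** Section 16.1.1 defines the response rate as the proportion of subjects with a confirmed complete or partial response. Section 11.1.1 treats a participant as evaluable for target disease response only if measurable disease was present at baseline.

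**The concern.** The same node of 10 to under 15 mm is measurable when the patient is screened and non-measurable when response is read. If it is the patient's only disease, the patient meets the wording of 3.1.2 but enters the trial with an empty target-lesion list, so the main way of responding is closed.

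The trial's conclusion rests on small counts: at least 3 responders among 18 to continue and at least 7 among 35 to call the regimen worthy of further study (16.2). One patient whose response is judged on a different scale from the others can matter at those cut-offs.

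**Working it through.** **Step 1: trace one patient through the rules.** Take a patient whose only disease is one 12 mm (short axis) node on CT.

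| Rule | Section | Result |
|---|---|---|
| Entry limit 10 mm, nodes by short axis | 3.1.2 | 12 ≥ 10: measurable, eligible |
| Node limit 15 mm short axis | 11.1.2 | 12 < 15: non-measurable |
| Target lesions come from measurable lesions | 11.1.2 | none |
| Partial response needs a target-lesion sum | 11.1.4.1 | cannot be met |
| Non-measurable disease table | 11.1.4.4 | CR, non-CR/non-PD, not evaluated or PD |
| Evaluable for target disease response | 11.1.1 | no |
| Denominator is subjects | 16.1.1 | apparently yes |

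**Step 2: what a complete response takes.** For non-target nodes, 11.1.4.2 requires a short axis below 10 mm, with marker normalisation if markers were raised. Percentage shrinkage = (baseline − follow-up) / baseline:

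- 10 to 9 mm: 1/10 = 10%
- 12 to 9 mm: 3/12 = 25%
- 14 to 9.9 mm: 4.1/14 = 29%

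The 30% line is reached at 10/0.7 = 14.3 mm. Measured in decimals, a node below about 14.2 mm can thus cross into complete response with less shrinkage than a target lesion needs for partial response. Recorded in whole millimetres, 13 to 9 mm is 4/13 = 31%, so the advantage is then confined to nodes of 12 mm or less. Marker normalisation and confirmation work against it.

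**Step 3: the design as stated.** Inputs from 16.2: 18 then 17 patients, cut-offs 3 and 7, null 10%, alternative 30%. (The Schema words the first-stage rule differently; 16.2 and 16.4 are used here.)

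P(success) = Σ over x ≥ 3 of Bin(x; 18, p) × P(Bin(17, p) ≥ 7 − x)

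- p = 0.10: 0.0474, which reproduces the stated 0.047.
- p = 0.30: 0.9016. The stated 95% does not reproduce. That is a separate matter; 90.2% is the baseline below.

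**Step 4: one affected patient, as bounds.** The documents give no number of such patients and no chance of complete response, so both are assumptions.

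*Never responds, and is counted.* Replace 18 by 17 (patient in stage 1) or 17 by 16 (patient in stage 2) and keep the cut-offs:

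- stage 1: power 0.8786, type I error 0.0403
- stage 2: power 0.8917, type I error 0.0423

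*Always reaches confirmed complete response.* In stage 1, the other patients need 2 of 17 and then 6 in total: power 0.9553, type I error 0.1108.

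For a stage 1 patient with chance q of complete response, the result is (1 − q) × first bound + q × second bound. Check: q = 0.30 at p = 0.30 gives 0.7 × 0.8786 + 0.3 × 0.9553 = 0.9016, the baseline. At p = 0.10, q = 0.30 gives 0.7 × 0.0403 + 0.3 × 0.1108 = 0.0615, above the 5% limit. The direction therefore depends on q, which is unknown.

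**The case against.** The strongest reply is that 3.1.2 ends by sending the reader to Section 11. Section 11.1.2 is built the same way, with a general 10 mm sentence followed by a separate node rule, so 3.1.2 could be read as repeating the general sentence and leaving nodes to Section 11. For external sites, the Coordinating Center also checks screening radiology reports and eligibility before registration (4.4; Appendix D, 3.5). This makes the gap less likely to bite. It does not close it: 3.1.2 presents its numbers as the definition, applies them to the nodal short axis by name, and points to a section with a different number without saying which prevails.

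A second reply is that few patients will have only small nodes. That is fair. The documents give no count, and with none enrolled the effect is nil.

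Two stronger readings are tempting, and the documents support neither.

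- **That the mismatch must lower the chance of meeting the 3 and 7 cut-offs.** This would need affected patients to respond less often than the others. They lose partial response, but on size alone their complete response can be easier to reach (step 2). The bias could run either way.
- **That sites would choose target lesions Section 11 disallows.** Section 3.1.2 says nothing about choosing target lesions. Those rules stand only in Section 11, so a site selecting target lesions is already working from the 15 mm limit.

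**Conclusion.** The two sections contradict each other as written and must be reconciled. Followed literally, 3.1.2 admits patients with only nodes of 10 to under 15 mm, who have no target lesion, cannot have a partial response, and can count as responders only through a complete response that may turn on about 1 mm. Their status in the denominator is open between 11.1.1 and 16.1.1.

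The textual finding is certain; its size is not. The loss from 90.2% to 87.9% or 89.2% power is a worst case for one patient. It assumes zero response, no replacement, and a 30% response rate in the others. Since the cut-offs are counts, dropping that patient from the denominator without replacement gives the same power. The opposite bound shows that the type I error could rise instead. With probably few such patients, this is a modest threat to the primary endpoint, but it is cheap to remove.

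**What to change.** Amend 3.1.2 so that a nodal lesion counts as measurable only if it meets the 11.1.2 short-axis threshold (15 mm by CT), and keep 10 mm longest diameter for non-nodal lesions on CT, MRI or calipers. Make the same change in the eligibility checklist. This uses the protocol's own response rule and alters no sample-size figure.

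The amendment acts only on later enrolments. If any patient with only small nodes is already in the trial, 16.1.1 should state, before responses are analysed, whether that patient is in the denominator.

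The cost is one clause and a checklist revision. The downside is that a rare patient whose only disease is small nodes is excluded.

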3.1.6 ECOG performance status ≤ 1 (Karnofsky $\geq 60\%$, see Appendix A)

3.1.7 Participants must have normal organ and marrow function as defined below:

- absolute neutrophil count	$\geq 1,500/\text{mcL}$
- platelets	$\geq 100,000/\text{mcL}$
- total bilirubin	$\leq 1.5 \times$ institutional upper limit of normal (ULN) (or $2.0 \times$ ULN in patients with documented Gilbert's Syndrome)
- AST (SGOT)/ALT (SGPT)	$\leq 2.5 \times$ ULN or $\leq 3 \times$ ULN for participants with documented liver metastases
- creatinine	$< 1.5 \times$ ULN
Or	
creatinine clearance	$\geq 40 \text{ mL/min}$ (using Cockcroft-Gault formula) for participants with creatinine levels above institutional normal
- Urine protein/creatinine ratio (UPCR)	≤ 1
- PT/INR or partial thromboplastin time (PTT) test	$< 1.3 \times$ the laboratory ULN within 7 days before the first dose of study treatment.

3.1.8 Negative urine pregnancy test for women of childbearing potential.

3.1.9 Participant must be able to swallow pills.

3.1.10 The participant is capable of understanding and complying with the protocol and has signed the informed consent document.

3.2

Exclusion Criteria

- 3.2.1 Major surgery (eg, GI surgery, removal or biopsy of brain metastasis) within 8 weeks before first dose of study treatment. Complete wound healing from major surgery must have occurred 1 month before first dose and from minor surgery (eg, simple excision, tooth extraction) at least 10 days before first dose. Subjects with clinically relevant ongoing complications from prior surgery are not eligible.
- 3.2.2 Participants who are receiving any other investigational agents.
- 3.2.3 Participants who have received a prior cabozantinib.
- 3.2.4 Participants who have received prior therapy with an anti-PD-1, anti-PD-L1, anti- PD-L2, anti-CD137, or anti-Cytotoxic T-lymphocyte-associated antigen-4 (CTLA-4) antibody (including nivolumab, pembrolizumab, ipilimumab, and any other antibody or drug specifically targeting T-cell co-stimulation or checkpoint pathways)
- 3.2.5 Participants with known Central Nervous System(CNS) metastases should be excluded from this clinical trial because of their poor prognosis and because they often develop progressive neurologic dysfunction that would confound the evaluation of neurologic and other adverse events.
- 3.2.6 The participant has tumor in contact with, invading, or encasing major blood vessels or radiographic evidence of significant cavitary pulmonary lesions.
- 3.2.7 History of allergic reactions attributed to compounds of similar chemical or biologic composition to cabozantinib or nivolumab.
- 3.2.8 Participants receiving any strong inhibitors or inducers of CYP3A4 within 14 days prior to registration are ineligible. Chronic treatment with strong inhibitors or inducers of CYP3A4 is not allowed.
- 3.2.9 Cardiovascular disorders including:
 - Congestive heart failure (CHF): New York Heart Association (NYHA) Class III (moderate) or Class IV (severe) at the time of screening;
 - Concurrent uncontrolled hypertension defined as sustained blood pressure (BP) > 150 mm Hg systolic or > 100 mm Hg diastolic despite optimal antihypertensive treatment within 7 days of the first dose of study treatment;
 - Any history of congenital long QT syndrome;
 - QTcF interval >500 msec
 - Any of the following within 6 months before the first dose of study treatment:
 - unstable angina pectoris;
 - clinically-significant cardiac arrhythmias;

- stroke (including transient ischemic attack (TIA), or other ischemic event);
- myocardial infarction;

3.2.10 GI disorders particularly those associated with a high risk of perforation or fistula formation including:

- Tumors invading the GI tract, active peptic ulcer disease, active inflammatory bowel disease (eg, Crohn's disease), active diverticulitis, cholecystitis, symptomatic cholangitis or appendicitis, acute pancreatitis or acute obstruction of the pancreatic duct or common bile duct, or gastric outlet obstruction
- Abdominal fistula, GI perforation, bowel obstruction, intra-abdominal abscess within 6 months before screening

3.2.11 Thromboembolic events within 6 months of registration.

Note: Low dose aspirin \leq 81 mg/day is allowed. Anticoagulation with therapeutic doses of LMWH is allowed in patients who are on a stable dose of LMWH for at least 6 weeks prior to registration. Treatment with warfarin is not allowed.

3.2.12 The subject has experienced any significant bleeding episodes, including:

- Clinically significant gastrointestinal bleeding within 6 months before the first dose of study treatment
- Clinically significant hemoptysis (> 0.5 teaspoon) within 3 months of the first dose of study treatment
- Any other signs indicative of pulmonary hemorrhage within 3 months before the start of study treatment
- Individuals with a history of different malignancy are ineligible except for the following circumstances: Individuals with a history of other malignancies are eligible if they have been disease-free for at least 3 years or are deemed by the investigator to be at low risk for recurrence of that malignancy.

- 3.2.13 Participant has an active infection requiring IV antibiotics
- 3.2.14 Any active, known, or suspected autoimmune disease. Participants with type I diabetes mellitus, hypothyroidism only requiring hormone replacement, skin disorders (such as vitiligo, psoriasis, or alopecia) not requiring systemic treatment, or conditions not expected to recur in the absence of an external trigger (e.g. celiac disease) are permitted to enroll.
- 3.2.15 Patient has a medical condition that requires chronic systemic steroid therapy or on any other form of immunosuppressive medication. Adrenal replacement steroid disease are permitted in the absence of autoimmune disease.
- 3.2.16 The participant is known to be positive for the human immunodeficiency virus (HIV), HepBsAg, or HCV RNA. HIV-positive participants with non-detectable viral loads on combination antiretroviral therapy are ineligible because of the potential for pharmacokinetic interactions with cabozantinib and nivolumab.
- 3.2.17 The participant has received a live vaccine within 28 days prior to the first dose of trial treatment and while participating in the trial. Examples of live vaccines include, but are not limited to, the following: measles, mumps, rubella, varicella/zoster, yellow fever, rabies, BCG, and typhoid vaccine. The use of the inactivated seasonal influenza vaccine (Fluzone®) is allowed.
- 3.2.18 Pregnant or lactating females are excluded from this study because cabozantinib and nivolumab are agents with the potential for teratogenic or abortifacient effects. Because there is an unknown but potential risk for adverse events in nursing infants secondary to treatment of the mother with cabozantinib and nivolumab, breastfeeding should be discontinued if the mother is treated with cabozantinib and nivolumab. These potential risks may also apply to other agents used in this study.
- 3.2.19 Sexually active fertile subjects and their partners must agree to use medically accepted methods of contraception (eg, barrier methods, including male condom, female condom, or diaphragm with spermicidal gel) during the course of the study and following treatment. Women of childbearing potential receiving nivolumab will be instructed to adhere to contraception for a period of 5 months after the last dose of nivolumab. Men receiving nivolumab and who are sexually active with WOCBP will be instructed to adhere to contraception for a period of 7 months after the last dose of nivolumab. Contraception must be used for 4 months after last dose of cabozantinib.

3.3

Inclusion of Women and Minorities

Both men and women of all races and ethnic groups are eligible for this trial.

4 REGISTRATION

4.1 General Guidelines for DF/HCC Institutions

Institutions will register eligible participants in the Clinical Trials Management System (CTMS) OnCore. Registrations must occur prior to the initiation of any protocol-specific therapy or intervention. Any participant not registered to the protocol before protocol-specific therapy or intervention begins will be considered ineligible and registration will be denied.

An investigator will confirm eligibility criteria and a member of the study team will complete the protocol-specific eligibility checklist.

Following registration, participants may begin protocol-specific therapy and/or intervention. Issues that would cause treatment delays should be discussed with the Overall Principal Investigator (PI). If the subject does not receive protocol therapy following registration, the subject must be taken off-study in the CTMS (OnCore) with an appropriate date and reason entered.

4.2 Registration Process for DF/HCC Institutions

Applicable DF/HCC policy (REGIST-101) must be followed.

4.3 General Guidelines for Other Investigative Sites

Eligible participants will be entered on study centrally by the Project Manager at the Coordinating Center. All sites should call the Project Manager at [contact] to verify dose level availabilities. The required Registration Request Cover Sheet and External Site Subject Registration forms will be provided to sites. Following registration, participants should begin protocol therapy within 5 days.* Issues that would cause treatment delays should be discussed with the Sponsor-Investigator. If the subject does not receive protocol therapy following registration, the subject must be taken off study in the CTMS (OnCore) with an appropriate date and reason entered.

4.4 Registration Process for Other Investigative Sites

To register a participant, the following documents should be completed by the participating site and faxed to [contact] or e-mailed to the Project Manager,
[contact]:

- Signed participant consent form
- HIPAA authorization form
- Eligibility Checklist
- Registration Request Coversheet
- External Site Subject Registration form

- Screening provider note including medical/ surgical history, ECOG performance status, vital signs, and physical exam findings
- Pathology report to support inclusion criteria
- Laboratory reports including:
 - CBC with differential
 - Chemistry panel
 - Pregnancy test (if applicable)
 - Thyroid panel
 - Coagulation panel
 - LDH
- Screening radiology reports (CT and/or MRI scans)
- Screening EKG

The participating site will then call [contact] or e-mail [contact], the Project Manager to verify eligibility. The Project Manager will follow DF/HCC policy (REGIST-101) and register the participant on the protocol. The Project Manager will fax or e-mail the participant study number and confirmation of registration to the participating site. The participating site will then register the patient per their local requirements.

